**Table 2: ASEPSIS Score**

Wound Characteristic	Proportion of Wound Affected										
	0	<20	20-39	40-59	60-79	>80					
Serous Exudate	0	1	2	3	4	5					
Erythema	0	1	2	3	4	5					
Purulent Exudate	0	2	4	6	8	10					
Separation of Deep Issue	0	2	4	6	8	10					
Points are scored for daily wound inspection.											
Additional Treatment		Points									
Antibiotics		10									
Drainage of Pus under local anesthesia		5									
Debridement of Wound (General Anesthesia)		10									
Serous Discharge*		Daily 0-5									
Erythema*		Daily 0-5									
Purulent Exudate*		Daily 0-10									
Separation of Deep Tissues*		Daily 0-10									
Isolation of Bacteria		10									
Stay as In-patient Prolonged Over 14 Days		5									
*Given scores on 5 of 7 days and the highest weekly score used.											
Category of Infection											
Total Score**		Definition									
0-10		Satisfactory Healing									
11-20		Disturbance of Healing									
21-30		Minor Wound Infection									
31-40		Moderate Wound Infection									
>40		Severe Wound Infection									
**Total Score calculated adding scores for individual wound characteristics and additional treatment.											

**Table 3: Acute Inflammatory Response Evaluation (AIRE) Score**

Score	Erythema	Oedema	Pain	Temperature
0	None observed	None observed	None	None
1	Slight blanching redness along incision closure line	Slight increase in tissue firmness (turgor)	Pain at site with pressure	Slightly warmer compared to adjacent skin
2	Moderate redness extending < 2 mm	Pitting of skin around incision with mild pressure	Pain at site with touch	Definitely warmer compared to adjacent skin
3	Intense redness extending > 2 mm	Tense firmness of skin around incision	Continuous pain	Radiating heat at incision site

## 3.0 Investigational Plan

### 3.1 Overall Study Design and Plan-Description

This is a multicenter, single blind prospective, randomized controlled study in patients undergoing elective TKA and meeting the study's eligibility criteria. Eligible patients will be randomized on 1:1 basis to have the surgical incision closed with either [REDACTED] or conventional sutures. The plan is to randomize at least 92 subjects for each of the two groups into this study in about 8 sites. Wound closure and surgical procedure times will be determined perioperative. Patients will remain blinded to the type of sutures utilized for closure of the incision.

### 3.2 Study Population

#### 3.2.1 Inclusion Criteria

Subjects satisfying the following criteria will be considered eligible for enrollment in this study:

1. Patient is  $\geq 18$  and  $< 80$  years of age;
2. Patient with osteoarthritis is scheduled to undergo elective unilateral TKA;
3. Patient is willing to participate in the study, comply with study requirements, follow-up schedule, and give written informed consent; and
4. Patient agrees not to schedule any additional elective surgical procedures until participation in this study is complete.

#### 3.2.2 Exclusion Criteria

Subjects meeting any of the following criteria will not be eligible for enrollment:

1. Female patient who is pregnant or lactating at the time of screening;
2. Patient has a Body Mass Index (BMI)  $> 40$  kg/m^2;
3. Patient is not able to walk independently (inability to walk at least 10 consecutive meters without a walking aid);
4. Patient has had a surgical intervention during the past 30 days for treatment of painful joint or its underlying etiology;
5. Patient has had previous open surgeries on the affected joint other than arthroscopy;
6. Patient has active infectious collagen diseases (i.e. scleroderma) or any other condition that would interfere with wound healing;
7. Patient is allergic to poly (p-dioxanone), IRGACARE®\* MP (triclosan) or D&C Violet No. 2;
8. Patient has diabetes with fasting plasma glucose (FPG)  $\geq 10.0$  mmol/L;
9. Patient has a history of immunosuppressive drug use, including steroids, within the last 6 months;
10. Patient has undergone chemotherapy or radiation within the last 6 months prior to study enrollment or is scheduled to do so during the study period;
11. Patient has known personal or family history of keloid formation or hypertrophy;
12. Patient has other dermatologic conditions known to impair wound healing;
13. Patient is participating in any other investigational drug (within 30 days or 5 half-lives of an investigational drug) or device study;
14. Patient has any physical or psychological condition which would impair study participation; and
15. Patient is judged unsuitable for study participation by the investigator for any other reason.

#### 3.2.3 Removal of Subjects from Study

In accordance with the current revision of the Declaration of Helsinki, a subject has the right to withdraw from the study at any time for any reason without prejudice to their future medical care by the physician or the institution. Should a subject (or subject's legally authorized guardian/representative) decide to withdraw, 1) all data collected up to the point of withdrawal will be considered for analysis; and 2) all efforts will be made to collect and report the final visit observations as thoroughly and timely as possible. The primary reason for early withdrawal will be recorded in the electronic case report form (eCRF), as such:

#### **Adverse Event**

When the subject experiences an AE and the PI or Medical Monitor believes it is in their best interest to discontinue participation in the study, the subject will be withdrawn from the study.

#### **Withdrawal of consent**

Any method of contact with the subject in which they state they no longer want to participate in the study specific activities constitutes withdrawal of consent for participation in the study. When possible, the reason for withdrawal will be documented.

#### **Site Termination or Study Termination**

A study site or the entire study may be terminated. When this occurs, all subjects currently enrolled at the site will be withdrawn and documented as early terminations. Reasons for site or study termination may include, but are not limited to the following:

- Administrative Concerns (e.g., inadequate subject enrollment, Investigator/institution non-compliance, change of business strategy, etc.);
- Safety Issues, including those due to non-compliance, which substantially affect the risk to benefit ratio of the study subjects at a site or for the study as a whole; or
- Regulatory Body Mandate(s).

#### **Death**

- When possible, the cause of death will be documented.

#### **Other**

- Either deep or intermediate layer can't be closed by one [REDACTED] suture;
- PI believed the incision is not suitable to be closed by absorbable suture (e.g., the tissue where prolonged (beyond six weeks) approximation of tissue under stress is required).

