## SCHEDULE OF EVENTS

Event	Visit 1	Visit 2	Visit 3	Visit 4	Visit 5
	Baseline/ Screening a	Randomization	Procedure	Post-Op through Discharge b	30-42 days c (post procedure)
Informed consent	X				
IWRS/IVRS d		X			
Inclusion/Exclusion Criteria	X	X			
Urine/blood pregnancy test	X				
Demographics	X				
Medical/Surgical history	X		X		
Physical examination e	X			X	X
Knee pain VAS	X			X	X
EQ-5D-3L	X			X	X
Concomitant medications f	X	X	X	X	X
Length of stay g				X	
Health Economic Data Collection				X	
Procedural data h			X		
Adverse events			X	X	X
Wound complication assessment			X	X	X
SSI/ASEPSIS score i				X	X
AIRE score				X	X
Study completion					X

- a. To be performed within 30 days of surgery.
- b. Physical examination, knee pain VAS, EQ-5D-3L and AIRE score will be collect on 3-5 days after surgery.
- c. Unless withdrawn from the study, subject's status will be confirmed at the time of in-person visit at 30-42 days following surgery. If possible, an in-person visit will be scheduled to confirm status for patients withdrawn prematurely from the study for any reason.
- d. Interactive web response system/ Interactive voice response system.
- e. The physical examination at baseline/screening visit includes height, weight and ROM of knee, and the post-procedure physical examination only includes ROM of knee.
- f. Including pain medications and antibiotics (except for anesthesia medications).
- g. Defined as time between procedure and discharge.
- h. Procedure time, overall OR time, intra-operative device failure rates, operating room resource utilization (if applicable), and anesthesia method (e.g., general or lumbar anesthesia).
- i. ASEPSIS score will be applied only after SSI confirmed.

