##### Wound Closure Procedure:

The wound closure will be performed at genuflex position.

For patients randomized to receive barbed sutures, the deep layer and the intermediate layer will be repaired and closed by using one [REDACTED] suture respectively. The

ratio of incision length to suture length for both layers is recommended to be no higher than 1:3. For patients randomized to receive conventional sutures, [REDACTED] sutures will be used to close the deep and the intermediate layers with interrupted suturing manner. Then for both groups, [REDACTED] sutures will be used to close the intradermal layer and the [REDACTED] Skin Closure System, a topical skin adhesive (TSA) will be applied to the skin surface to tissue approximation. Please find the details in Table 4,5.

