#### **6.1.3 Adverse Event**

An AE is defined as any untoward medical occurrence, regardless of its relationship to the study device (study suture) or the study procedure (TKA). An untoward medical occurrence includes any new, undesirable medical experience or worsening of a pre-existing condition, which occurs at any point from the surgery to Final Visit.

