### **6.2 Reporting Adverse Events**

Investigators are required to report all AEs experienced by subjects from the time of enrollment (defined as first incision) until the subject completes the study or terminates early. All AEs, regardless of their relatedness to the study device, must be reported in the AE eCRF. The investigator will evaluate the intensity of the event, severity of the event, and its relatedness to the study device or procedure,. Any necessary medical management of the event will be recorded in the subject's medical record/source document. All AEs must be followed until resolution or until they become stable but ongoing.

The sponsor will follow CFDA's guideline to request sponsor to report the safety events including SAE/AE with timeline, which is regulated by law.

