2.2 DEFINITIONS OF ANALYSIS SETS

There will be three analysis sets defined:

- Modified Intent-to-treat set (mITT set) consists of all randomized subjects who had the surgical incisions closed using the randomized suture
- Evaluable [or Per-Protocol (PP)] set consists of all mITT subjects who have no major protocol violations.
- Safety set consists of all subjects who receive surgery.

Major protocol deviations are deviations that have an impact on the primary endpoint, or that have an impact on the randomization assignment. These will be determined prior to database lock.

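### Treating failure to close a layer with one suture as withdrawal from the study can shorten safety follow-up in the barbed arm alone, so harm in that arm may be understated

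*Protocol*

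**What the plan says.** **Removal.** Protocol 3.2.3 says that the primary reason for early withdrawal is recorded in the eCRF and then lists the reasons. Under 'Other' there are two: that "Either deep or intermediate layer can't be closed by one" suture, and that the "PI believed the incision is not suitable to be closed by absorbable suture".

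**Closure.** Protocol 3.3.1 states: "For patients randomized to receive barbed sutures, the deep layer and the intermediate layer will be repaired and closed by using one" suture for each. The control arm is closed in these layers with interrupted sutures, and no one-suture limit is set.

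**AE reporting.** Protocol 6.2 asks for AEs "from the time of enrollment (defined as first incision) until the subject completes the study or terminates early". It adds that "All AEs must be followed until resolution or until they become stable but ongoing". Protocol 6.1.3 and SAP 3.3.2 define an AE as an occurrence "which occurs at any point from the surgery to Final Visit".

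**Visits after withdrawal.** Footnote c of the Schedule of Events (repeated in SAP Table 4) requires status confirmation at 30-42 days except for withdrawn subjects. For those it says: "If possible, an in-person visit will be scheduled to confirm status for patients withdrawn prematurely from the study for any reason". Protocol 3.2.3 also asks for every effort to obtain final-visit observations, in a sentence about a subject who decides to withdraw.

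**Analysis.** SAP 2.2 states: "Safety set consists of all subjects who receive surgery". Protocol 4.5.5 and SAP 3.3 summarize safety descriptively on available data, without imputation.

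**The concern.** The trigger is a post-randomization event tied to how the study device performed, and the surgeon who judges it is not blinded. It belongs in practice to one arm. If it counts as early termination, the duty to report new AEs can end on the day of surgery for the barbed subjects whose closure was difficult. The subject nevertheless stays in the Safety set.

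Comparing the safety profiles of the two closure methods is a stated objective (Protocol 2.0, SAP 1.1.3). Infection, dehiscence, delayed healing and wound-related AEs mostly appear after the operation. If they go unobserved more often in one arm, the descriptive comparison tilts towards that arm, and events that were never collected cannot be recovered at analysis.

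**Working it through.** **The plan's own figure.** 77 evaluable per arm with 16% withdrawal gives 77 / (1 - 0.16) = 91.67, rounded up to 92, as stated. The effect size is redacted. With SD 8 (Protocol 4.5.2), one-sided 0.025 and 90% power, a two-sample t-test gives 77 if the reduction is about 25% of 16.89 minutes (SAP 1.3.3), that is 4.22 minutes. The sample size is therefore sound and neither supports nor weakens this point. It supplies N = 92.

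**Does the reason belong to one arm?** The product name in the first 'Other' item is redacted. The one-suture condition matches only the barbed-arm instruction in 3.3.1, so the first item is in effect specific to that arm. The second item refers to absorbable suture in general and is not.

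**Is follow-up cut?** Set side by side:
- 6.2 stops the reporting duty at early termination, while 6.1.3 runs the AE definition to the final visit. For a subject withdrawn at closure, the two windows differ by the whole post-operative period.
- Following AEs to resolution applies to events already known. It does not require anyone to look for a new one.
- Footnote c covers withdrawal for any reason, but only as a status visit where possible.
- Visit 4 is neither cancelled nor continued for these subjects.

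**How large could the effect be?** All three inputs are assumptions, because the documents give none of them:
- w = barbed subjects withdrawn at closure
- r = their event risk relative to other barbed subjects
- c = share of their events still captured

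If everyone is in the denominator, the underlying event rate cancels:

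reported / true = [(92 - w) + c·r·w] / [(92 - w) + r·w]

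| w | r | c | Calculation | Ratio |
|---|---|---|---|---|
| any | any | 1 | numerator = denominator | 1.00 |
| 2 | 1 | 0 | 90/92 | 0.98 |
| 5 | 1 | 0 | 87/92 | 0.95 |
| 5 | 3 | 0.5 | 94.5/102 | 0.93 |
| 5 | 3 | 0 | 87/102 | 0.85 |
| 15 | 3 | 0 | 77/122 | 0.63 |

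The last row is extreme: 15 = 92 - 77 gives the whole withdrawal allowance in that arm to this one cause.

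If unobserved subjects are instead shown as missing and left out of the denominator (c = 0), the ratio is 92 / [(92 - w) + r·w]. With w = 5 this is 92/92 = 1.00 at equal risk and 92/102 = 0.90 at threefold risk. A denominator of subjects assessed removes the dilution but not the selective loss.

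In events, at an assumed 5% rate with w = 5 and c = 0, the number missed is 5 × 0.05 = 0.25 at equal risk and 5 × 0.15 = 0.75 at threefold risk. In the second case the reported incidence is 4.35/92 = 4.7%, against a true 5.10/92 = 5.5%.

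**The case against.** The strongest reply is that the text leaves more follow-up in place than a quick reading suggests, and much of it stands.

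- A reader might infer that Visit 4 is dropped for these subjects. No section says so, and 3.3.1 has every patient's status monitored until discharge. The documents are silent on the visit, which is a gap but not a cancellation.
- A reader might infer that barbed-arm harm *is* understated. That needs incomplete capture. The status visit, the effort to obtain final-visit data and the AE definition all work against it, and Visit 3 already records intra-operative AEs, wound complications and device failures. With full capture there is no bias.
- A reader might infer that these subjects are certain to dilute the percentages. The available-data wording in SAP 3.3, and the reporting of numbers missing in SAP 2.1, allow them to be shown as missing. For AIRE and ASEPSIS means, a subject without data drops out of n. Neither document says whether the Safety set is grouped as randomized or as treated. If as treated, such a subject may not be counted in the barbed arm at all.
- Withdrawal is listed as a recordable reason, without the explicit statement of removal used for AEs or site termination. The section heading favours reading it as removal, but the wording is not firm.
- The event may be rare: 3.3.1 recommends limits on incision length and on the ratio of incision to suture length. Safety is also descriptive, so no test or decision rule depends on it.

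This removes any claim of certain or large bias. It does not remove the one-sided trigger, the early end of the reporting duty in 6.2, or the conditional nature of the remaining visit.

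**Conclusion.** The point holds as a risk. As written, the plan allows safety follow-up to be shortened after a difficult barbed closure, with no counterpart in the control arm, while the subject remains in the Safety set. Barbed-arm incidence may therefore be understated. Its size cannot be known from the documents. It is zero with full capture, or where unobserved subjects are shown as missing and carry equal risk. It is about 5% relative with 5 of 92 subjects, no capture, equal risk and all in the denominator, and about 15% if their risk is threefold. Larger values need extreme inputs. Only the first 'Other' reason is specific to one arm. This is a worthwhile and inexpensive correction; it does not threaten the primary conclusion and is not a condition for the trial to proceed.

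**What to change.** - **Protocol 3.2.3:** record both 'Other' items as *assigned closure not used or not completed*, not as withdrawal from the study. State that these subjects remain on Visits 4 and 5 with all scheduled assessments.
- **Protocol 6.2:** continue AE reporting to the final visit for every operated subject, in line with 6.1.3 and SAP 3.3.2. End it early only for withdrawal of consent, death, loss to follow-up, or site or study termination. Align footnote c of the Schedule of Events.
- **SAP 3.3:** report by arm how many Safety-set subjects have Visit 4 and Visit 5 safety data. Use subjects assessed as the denominator for visit-assessed incidences.
- **SAP 2.2:** state whether the Safety set is grouped as randomized or as treated.

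The cost is amendment wording, a few SAP lines and some extra CRF pages. The visits are already planned for every subject. Nothing here prescribes how a wound should be closed or when the closure method should change.

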### **3.3 Study Procedure**

#### **3.3.1 Procedure Description**

##### TKA Surgical Procedure:

It is suggested that no more than two surgeons at each would investigative site perform the wound closure procedure of TKA to minimize bias and variability. The TKA procedure will be performed per each institutional requirements or specific guidelines with a median incision. The length of incision is recommended to be no longer than 15 cm.

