**Table 5: Wound closure procedure and devices in control group**

Layer	Suture Material	Suture Technique	Code
Deep layer	[REDACTED]	Interrupted	[REDACTED]
Intermediate layer	[REDACTED]	Interrupted	[REDACTED]
Intradermal layer	[REDACTED]	Continuous	[REDACTED]
Skin layer	[REDACTED]	N/A	[REDACTED]

The sutures and TSA will be used per the Instructions for Use [21-24]. Surgeons must be familiar with surgical procedures and techniques involving absorbable sutures as risk of wound dehiscence/separation may vary with the site of application and the suture material used. Consequently, surgeons must consider the in vivo performance when evaluating the eligibility of potential subjects for enrollment into the study. The use of an absorbable suture may be inappropriate in elderly, malnourished, or debilitated patients, or in patients suffering from conditions which may delay wound healing.

Postoperative Care:

Postoperative care will be performed per institutional requirements ROM exercises will be performed adhering to institutional requirements and specific guidelines regarding postoperative care. Patient status is monitored closely until discharge. Thrombolytic therapy beyond discharge can be continued prophylactically per intuition requirements or not. Changes in concomitant medications including analgesics will be recorded throughout inpatient stay.

Other – Health Economic Data Collection

In order to estimate the costs characteristics and influence factors, the following costs data will be collected if available:

Overall fee: Total fees, hospital stay fees, self-paid amount, etc  
 Comprehensive medical services costs, including general medical service charges, general treatment procedure fees, and nursing costs, etc.  
 Diagnosis fees, including pathological diagnosis fee, imaging diagnosis fee, clinical diagnosis fee, and laboratory diagnosis fee, etc.

Treatment fees, including non-operation treatment fee (clinical physical treatment fee), operation costs (anesthetic fee, procedure costs)  
Rehabilitation fee, including rehabilitation costs, etc.  
Medicines fee, including traditional Chinese medicine, western Chinese medicine, antibiotic fees, etc.  
Blood and blood products costs, including fees of blood, blood coagulation products, etc.  
Medical supplies costs, including fees of disposal medical supplies for examination, fees of disposal medical supplies for treatment, and disposal medical supplies for surgery, etc.  
The other costs, if applicable.

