#### **4.5.2 Determination of Sample Size**

The proposed sample size of 92 patients per arm (184 total) is considered adequate to test the hypothesis that [REDACTED] can reduce the time for incision closure compared to conventional sutures. Based upon a review of the literature, the mean incision closure time was assumed to be [REDACTED] minutes for conventional sutures, being calculated as a weighted (based on number of subjects) mean of the means observed in the studies reviewed. The studies reported incision closure times ranging between 14.4 to 26.5 minutes [5, 7-10]. It is expected that the [REDACTED] can reduce the incision closure time by [REDACTED] % compared to conventional sutures; therefore, the assumed mean closure time for [REDACTED] is [REDACTED] minutes. The standard deviations observed in the reviewed literature range from 3.43 to 8.5 minutes for the conventional sutures; the standard deviation for this study was conservatively assumed to be [REDACTED] minutes in both groups for several

reasons, such as the lack of data for [REDACTED] and that this patient sample may be older and with larger BMI. The distribution of incision closure time is assumed to be normal.

The statistical hypotheses for the primary endpoint are as follows:

- H0: Mean Barbed  $\geq$  Mean conventional suture tested against the alternative hypothesis
- Ha: Mean Barbed  $<$  Mean conventional suture;

Where:

- The assumed mean time to incision closure in conventional group is [REDACTED] minutes;
- The mean time to closure in [REDACTED] is [REDACTED] minutes;
- The assumed standard deviations in the two groups are both 8.

Based upon these assumptions, a total seventy seven (77) evaluable subjects per arm will achieve 90% power to detect a difference of [REDACTED] minutes (expected mean for [REDACTED] of [REDACTED] minutes and the conventional group of [REDACTED] minutes) with estimated group standard deviations of [REDACTED] using a one-sided two-sample t-test. The assumed one-sided significance level is 0.025.

If the higher limit of the one-sided 97.5% confidence interval for the difference in the Mean [REDACTED] time minus the Mean closure time for conventional suture is smaller than 0, then it will be concluded that [REDACTED] is considered to be superior to conventional suture. The sample size is adjusted to 92 per arm to account for a 16% withdraw rate [25-28].

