1.3.3 Sample Size and Statistical Power Considerations

The proposed sample size of 92 patients per arm (184 total) is considered adequate to test the hypothesis that [REDACTED] can reduce the time for incision closure compared to conventional sutures. Based upon a review of the literature, the mean incision closure time was assumed to be 16.89 minutes for conventional sutures, being calculated as a weighted (based on number of subjects) mean of the means observed in the studies reviewed. The studies reported incision closure times ranging between 14.4 to 26.5 minutes [4-8]. It is expected that the [REDACTED] can reduce the incision closure time by [REDACTED] compared to conventional sutures; therefore, the assumed mean closure time for [REDACTED] is [REDACTED] minutes. The standard deviations observed in the reviewed literature range from [REDACTED] to [REDACTED] minutes for the conventional sutures; the standard deviation for this study was conservatively assumed to be [REDACTED] minutes in both groups for several reasons, such as the lack of data for [REDACTED] and that this patient sample may be older and with larger Body Mass Index (BMI). The distribution of incision closure time is assumed to be normal.

The statistical hypotheses for the primary endpoint are as follows:

- H_0 : Mean Barbed \geq Mean conventional suture tested against the alternative hypothesis
- H_a : Mean Barbed $<$ Mean conventional suture;

Where:

- The assumed mean time to incision closure in conventional group is [REDACTED] minutes;
- The mean time to closure in [REDACTED] is [REDACTED] minutes;

- The assumed standard deviations in the two groups are both [REDACTED]

Based upon these assumptions, a total seventy-seven (77) evaluable subjects per arm will achieve 90% power to detect a difference of [REDACTED] minutes (expected mean for [REDACTED] of [REDACTED] minutes and the conventional group of [REDACTED] minutes) with estimated group standard deviations of [REDACTED] using a one-sided two-sample t-test. The assumed one-sided significance level is [REDACTED]

If the higher limit of the one-sided 97.5% confidence interval for the difference in the Mean [REDACTED] time minus the Mean closure time for conventional suture is smaller than 0, then it will be concluded that [REDACTED] is considered to be superior to conventional suture. The sample size is adjusted to 92 per arm to account for a 16% withdraw rate [9-12].

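### The closing surgeon need not be named before the arm is known and is not a listed data item, so arm-dependent choice of operator could bias closure time without any planned analysis showing it

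*Protocol*

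**What the plan says.** - **Endpoint and operator.** Protocol 2.1 and SAP 1.2.1 define the primary endpoint as suturing time, from the first deep throw to completion of the intradermal layer. Protocol 3.3.2 states that the surgeon cannot be blinded.
- **Who closes.** Protocol 3.3.1: "It is suggested that no more than two surgeons at each would investigative site perform the wound closure procedure of TKA". The reason given is to limit bias and variability, but the limit is advisory. Nothing says that the same surgeons must close in both arms.
- **When the arm is known.** Randomization is central and the next assignment cannot be guessed (Protocol 3.4, Randomization). It takes place at Visit 2, before the procedure (3.4.2). Neither place asks for the closer to be identified first.
- **What is recorded.** Footnote h of the Schedule of Events lists "Procedure time, overall OR time, intra-operative device failure rates, operating room resource utilization (if applicable), and anesthesia method". The Visit 3 list in 3.4.3.2 adds the code and quantity of the closure devices. Neither list includes the person who closed.
- **Skill.** Protocol 3.3.1: "Surgeons must be familiar with surgical procedures and techniques involving absorbable sutures". The products are to be used per their Instructions for Use, and Protocol 4.3 provides for qualified investigators and a review of procedures before the study.
- **Analysis.** The primary analysis is an unadjusted t-interval for the difference in means (Protocol 4.5.4; SAP 3.2.1.1). There is no centre adjustment (Protocol 4.6.2; SAP 2.5). No analysis by surgeon, site or case order is planned, and SAP 3.4 marks exploratory analysis as not applicable.

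**The concern.** Central concealment protects the selection of patients. It does not protect the selection of the operator once the arm is known. Between Visit 2 and closure, an unblinded team can decide, knowingly or not, that one technique goes to the faster or more senior of its closers. Because the endpoint is that person's speed, the choice feeds directly into the primary difference. It can favour the device or work against it.

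The trial makes one inferential claim, that the device is faster. An early question from any reader will be who sutured in each arm, and the listed data and planned tables do not answer it.

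**Working it through.** **Inputs from the documents**
- Protocol 4.5.2: "a total seventy seven (77) evaluable subjects per arm will achieve 90% power".
- Protocol 4.5.2: "The assumed standard deviations in the two groups are both 8" (minutes).
- Protocol 4.5.2: "The assumed one-sided significance level is 0.025".
- SAP 1.3.3: "the mean incision closure time was assumed to be 16.89 minutes for conventional sutures".
- 92 randomized per arm after a 16% withdrawal allowance (Protocol 4.5.2), at about 8 sites (Protocol 3.1).
- The target difference is blacked out and has to be back-solved.

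**Reproducing the plan**
- Withdrawal: 77 / (1 − 0.16) = 91.7, rounded up to 92. This matches.
- Standard error of the difference: 8 × √(2/77) = 1.289 min.
- Using the noncentral t with 152 degrees of freedom, the difference that gives 90% power at one-sided 0.025 is 4.21 min. As a plausibility check, 4.21 / 16.89 = 24.9%. An assumed 25% reduction (4.22 min) gives exactly 77 per arm.

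**Effect of operator choice**

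Bias = (gap between closers in minutes) × (difference between arms in the share closed by the faster one) × (share of the trial affected). The documents give none of these three, so all are assumptions. A 20-point difference means 60/40 in one arm and 40/60 in the other.

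The bias is entered as a shift in the noncentral t. The error column takes a true difference of 0 with the bias favouring the device. The power column takes a true difference of 4.21 min with the bias against it.

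| Assumed scenario | Net bias (min) | One-sided error, 77/arm | Power, 77/arm |
|---|---|---|---|
| None | 0 | 2.5% | 90% |
| 6-min gap, 20 points, one of 8 equal sites: 6 × 0.2 / 8 | 0.15 | 3.3% | 88% |
| 2-min gap, 20 points, all sites: 2 × 0.2 | 0.4 | 4.9% | 83% |
| 4-min gap, 20 points, all sites: 4 × 0.2 | 0.8 | 9.0% | 75% |
| 6-min gap, 20 points, all sites: 6 × 0.2 | 1.2 | 15% | 64% |

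The endpoint is measured during surgery, so later withdrawal need not remove it, and the analysed number may be nearer 92 per arm. Repeating the calculation with 92 gives power of 94% without bias, and 93% / 89% / 82% / 72% for the four biases. The one-sided error becomes 3.3% / 5.2% / 9.9% / 17%. More subjects restore some power but make the false-positive side worse, because the bias does not shrink with the sample size.

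**Early barbed cases (secondary)**

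Assume 8 × 2 = 16 closers, so 92 / 16 = 5.75 barbed cases each. If each closer's first two cases take 2 or 4 min longer, the barbed mean rises by 2 × 2 / 5.75 = 0.70 min or 2 × 4 / 5.75 = 1.39 min. Power at 77 per arm falls to 77% or 58%. The number of closers, the penalty and its duration are all assumed. The shift lengthens the barbed arm only.

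**The case against.** **The documents do not show that closers will be chosen by arm.** That stands. They only fail to prevent it, and they contain partial safeguards: concealed central allocation and the suggested two-closer limit. The supportable statement is that operator choice can enter the comparison.

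**A reader might infer that the problem could never be detected.** The documents do not support that. SAP 2.3.2 counts study days from the randomization date and SAP 3.1.1 tabulates enrolment by site and arm, so case order within site can be derived. Operation records are kept as source documents (Protocol 3.3.2 and 4.1.1) and may name the operator. The eCRF is not shown, so absence from the protocol lists does not prove absence from the database. But no planned analysis uses any of this, and retrieval afterwards would not prevent the bias.

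**The larger biases are demanding.** That also stands. A bias of 1.2 min needs a 6-minute gap and the same skew in the same direction at all sites. Confined to one site of eight it is 0.15 min, and skews in opposite directions cancel. The literature range of 14.4 to 26.5 min in Protocol 4.5.2 is a spread between studies and does not measure the gap between two surgeons at one site.

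**A reader might also infer that the surgeons lack barbed-suture experience.** The remark in Protocol 4.5.2 on missing data is a reason for a conservative standard deviation and says nothing about skill. All closure products are legally marketed in China (Synopsis), and the familiarity requirement covers absorbable sutures, which include the study device. Early cases could cost power, but they cannot by themselves create false superiority.

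**Conclusion.** The point holds as a gap in prevention and recording. The closer need not be fixed before the arm is known, and closer identity is not a listed data item. No planned analysis would show whether the operators differed between arms.

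Against an implied target of about 4.2 min, even a net bias of 0.4 min roughly doubles the one-sided error, from 2.5% to 4.9%, or takes power from 90% to 83%. At 1.2 min the figures are 15% and 64%. All of these rest on assumed operator gaps and imbalances, and the upper values require a consistent skew at most sites. They show how sensitive the result is and do not predict what will happen.

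The learning-curve issue is secondary. It works against the device and affects power only. Whether to require prior barbed cases is a design choice for the sponsor, since including early cases may reflect real adoption.

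**What to change.** 1. **Protocol 3.4.2:** require the site to enter the named closing surgeon in the IWRS before allocation is released, and record any later change of closer as a deviation.
2. **Schedule of Events footnote h and Protocol 3.4.3.2:** add closer ID to the Visit 3 procedural data.
3. **SAP 3.2.1:** add a supportive descriptive summary of closure time by arm within closer and site, and by case order. The case-order part is enough to cover the learning-curve question.

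The primary analysis and the sample size do not change. The cost is one IWRS field, one eCRF field, one supportive summary and somewhat less flexibility in theatre scheduling. Naming the closer in advance prevents the problem, whereas adjusting for closer afterwards would be a weaker substitute.
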